### 2.2. Secondary Objective

The secondary objective to assess the lung tumor and healthy tissue response to PDT.

---

### 3. STUDY DESCRIPTION

#### 3.1. Over all Study Description

This is a prospective, multicenter, uncontrolled, non-randomized, open-label, clinical study with the primary objective to assess safety of PDT in subjects with peripherally located malignant tumors in lung parenchyma prior to surgical resection. A Time and Procedures Schedule for the overall conduct of the study is outlined in Appendix 13-1.

The primary diagnosis will be performed as per standard of care no more than 60 days prior to consent signature. Upon signing consent, subjects will be assigned a unique participation number and will undergo screening evaluation conducted during the 30 days prior to enrollment. This phase will involve medical evaluations and thorough review of all reports that led to the primary diagnosis. Upon successful screening evaluations, subjects will be enrolled into the study.

Treatment Procedures will consist of one PDT-Photofrin® course performed through navigational bronchoscopy or peripheral ultrasound guided bronchoscopy. One course will consist of an intravenous (IV) injection of Photofrin® 2 mg/kg over 3-5 minutes followed by one laser light application. The end of injection will be Study Hour 0. Photodynamic laser therapy will be performed on Study Hour 40-50. Laser light (630 nm wavelength) will be applied at a dose of 200 J/cm of the diffuser length.

Ten to 15 days after PDT, subjects will undergo surgery as per standard of care. Macroscopic and microscopic examinations of the tumor and surrounding healthy lung tissue will be evaluated to determine the effect of PDT on the tumor and the healthy/non-tumor lung tissue. Macroscopic examinations will be performed at the local institution. Microscopic examinations will be performed by a central reader pathologist.

Follow-up assessments will include some or all the following procedures: physical exam; vital signs evaluation; body weight measurement; chest CT; chest X-ray; performance status; and clinical laboratory testing. All subjects will be asked general questions about the occurrence of adverse events, concurrent medical conditions, use of adjunctive therapy/procedure, and intake of concomitant medication.

Data will be analyzed to evaluate the safety of the modality up to 90 days.

#### 3.2. Scheduling of Visits

Pretreatment assessments will be performed during the 30 days prior to enrollment. After enrollment, study visits will be as follows:

- Study Day 0 will be the day the subject is enrolled.
- Study Day 1 will be the day of the PHO injection. Study Hour 0 will be the time of the end of PHO injection.
- Study Day 3 will be the day of PDT. Study Hour 40-50 will be calculated from Study Hour 0.
- Study Day 13 to Day 18 will be the time-period where the surgery will be performed post PDT.

- 
- Study Day 20 to Day 25 ( $\pm 2$  days) will be the 7-day post-surgery visit.
  - Study Day 43 to Day 48 ( $\pm 3$  days) will be the 30-day post-surgery visit.
  - Study Day 103 to Day 108 ( $\pm 7$  days) will be the 90-day post-surgery last study visit.

### 3.3. Estimated Duration of the Study

Time permitted for enrollment will be 9 months. Therefore, this study has an estimated duration of approximately 15 months.

Enrollment at all sites will be reviewed on an ongoing basis. After six months, if enrollment at any site falls below 50% of the projected total, the sponsor can exercise the right to terminate the study at that site.

The end of the clinical part of the study at any sites will be defined as the date of the last visit of the last active subject at that site. The official end of the clinical part of the study at all sites will be defined as the date of the last visit of the last active subject in the study. At the end of the clinical part of the study, subjects will be treated as per the investigator's judgment.

---

## 4. STUDY POPULATION

### 4.1. Primary Diagnosis

This study plans to enroll subjects with histologically or cytologically confirmation of peripherally located solid tumor in lung parenchyma. When applicable, subjects will be staged with chest CT and positron emission tomography (PET) scanning or as per local practice. Ideally subjects should have undergone an initial integrated whole body PET CT scan as part of their standard of care (SoC) staging protocol.

All procedures performed to confirm the primary diagnosis will be considered SoC and not research-related activities and will be performed no more than 60 days prior to ICF signature. Primary diagnosis will be based on the following assessments as per local practice and physician's clinical judgement to avoid unneeded procedures.

1. Confirmed solid tumor.
2. Either biopsy- or cytology-proven confirmation of primary or metastatic lung tumor of any subtype (e.g., adenocarcinoma, carcinoids, squamous cell carcinoma, large cell carcinoma, NOS [not otherwise specified], etc.).
3. Peripheral tumor location as defined by the Radiation Therapy Oncology Group protocols as the primary tumor not touching a 2-cm volume in all directions around the proximal bronchial tree (distal 2 cm of the trachea, main stem bronchi, and lobar bronchi). Tumors beyond the 3rd generation airways are included.
4. Tumor < 5 cm along any axis based on official radiology report.
5. Candidate for surgery.

### 4.2. Number of Subjects

This study plans to enroll up to approximately 10 subjects from about five US clinical research sites experienced in navigational bronchoscopy.

### 4.3. Eligibility Criteria

#### 4.3.1. Inclusion Criteria

In order to be eligible to participate in the study, potential subjects must meet all of the following inclusion criteria.

1. Male or female subject is eighteen years of age and older (but less than 80 years of age).
2. Subject is diagnosed with primary or metastatic tumor < 5 cm located in peripheral lung that can be completely resectable (R0).
3. Subject is a candidate for surgical resection.
4. Subject is a candidate for bronchoscopy.
5. The tumor is accessible for unrestricted illumination of PDT.

6. Subject is deemed likely to survive for at least 3 months.
7. Non-menopausal or non-sterile female subject of childbearing potential has a negative serum  $\beta$ -HCG at the time of entry into the study.
8. Non-menopausal or non-surgically sterilized female subject of childbearing potential uses a medically acceptable form of birth control.
9. Subject is able and willing to provide written informed consent to participate in the study, which must comply with the International Council for Harmonisation (ICH) guidelines and local requirements.

#### 4.3.2. Exclusion Criteria

Potential subjects who meet any of the exclusion criteria will not be allowed to enroll into the study.

1. Subject diagnosed with small cell lung cancers or carcinoid tumors.
2. Subject has a primary or metastatic lung tumor located within 2 cm of the proximal bronchial tree or within 2 cm of a major structure (e.g., aorta, heart, trachea, pericardium, superior vena cava, pulmonary artery, pulmonary vein, esophagus, spine).
3. Subject has a primary or metastatic lung tumor near the vertebral body.
4. The tumor invades a major blood vessel.
5. Subject with concurrent non-solid malignancy.
6. Subject has had previous direct radiation treatment (other than mediastinal radiation) on the tumor scheduled for resection.
7. Subject has had chemotherapy in the last four weeks.
8. Subject has received prior PDT on the tumor scheduled for resection during 3 months prior to the date of the ICF signature.
9. Subject with blood parameters of Grade 3 or higher on the Common Terminology Criteria for Adverse Events (CTCAE) 5-point scale; parameters of Grade 2 will be excluded if judged clinically significant by the investigator.
10. Subject with known porphyria or known hypersensitivity to Photofrin® or porphyrin-like compounds or to any of its excipients.
11. Subject with a coexisting ophthalmic disease likely to require slit-lamp examination within the next 90 days.
12. Subject with any acute or chronic medical or psychological illnesses as judged clinically significant by the investigator to preclude bronchoscopy procedures.
13. Female subject who is breastfeeding or intends to breastfeed during the study.
14. Subject who participated within the last 30 days, participates or intends to participate in another investigational study (other than observational studies) during the study.

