#### *5.2.1.2. PDT Bronchoscopy (Study Day 3, 40-50 Hours post Photofrin® injection)*

Subjects will return to the institution on Study Day 3 (40-50 hours post Photofrin® injection) for the PDT bronchoscopy procedure. The following assessments will be performed.

1. Vital signs (pulse, blood pressure, temperature, and respiration rate).
2. ECOG Performance Status.
3. Under general anesthesia or deep sedation
  - a. Subjects will undergo a flexible bronchoscopy with navigation guidance to confirm the location and the size of the lesion with the use of radial probe endobronchial ultrasonography (REBUS). This will be captured by video.
  - b. The investigator will select the optical fiber diffuser length to match the tumor length.
  - c. Once the desired placement of the probe is confirmed by REBUS, the investigator will remove the REBUS probe and will insert the selected optical fiber in the lesion under fluoroscopy guidance. This will be captured by video. Exceptionally, the placement of the diffuser adjacent to the tumor for intraluminal activation will be acceptable only if the placement of the optical diffuser in the lesion has been unsuccessful. For larger lesions than 1.5 cm the placement of multiple fibers from different directions will be allowed if feasible.
  - d. After the placement of the optical fiber in the lesion, the 630 nm PDT laser will be turned on and will deliver a light dose of 200 J/cm of diffuser length for an exposure time of 8 minutes and 20 seconds using a pre-set total power output. Subjects presenting multiple metastases, only one lesion would be treated.
4. Re-educate the subject on how to manage light exposure.
5. Record concomitant medications and adverse events.
6. Admit subject for a 48-hour hospitalization period.

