## 7. WARNINGS AND PRECAUTIONS

### 7.1. Phototoxicity Reactions

All subjects who receive Photofrin® will be photosensitive and must observe precautions to avoid exposure of eyes and skin to direct sunlight or bright indoor light (from examination lamps, including dental lamps, operating room lamps, unshaded light bulbs at close proximity, etc.) for at least 30 days or longer as per local labelling.

The level of phototoxicity will vary for different areas of the body, depending on the extent of previous exposure to light. Before exposing any area of skin to direct sunlight or bright indoor light, the subject should perform the Light Challenge to test the skin for residual phototoxicity. A small area of skin (e.g., hand) should be exposed to sunlight for 10 minutes. If no phototoxicity reaction (erythema, edema, blistering) occurs within 24 hours, the subject can gradually resume normal outdoor activities, initially continuing to exercise caution and gradually allowing increased exposure. If a phototoxicity reaction occurs with the limited skin test, the subject should continue the existing precautions for another 2 weeks before re-testing. As the tissue surrounding the eyes may be more sensitive, it is therefore not recommended that the face be used for testing. If subjects travel to a different geographical area with greater sunshine, they should retest their level of phototoxicity. Ultraviolet (UV) sunscreens are of no value in protecting against phototoxicity reactions because photoactivation is caused by visible light.

Some subjects may remain photosensitive for up to 90 days or more. The photosensitivity is due to residual drug, which will be present in all parts of the skin. Exposure of the largest possible area of skin to ambient indoor light is, however, beneficial because the remaining drug will be inactivated gradually and safely through a photobleaching reaction. Therefore, subjects should not stay in a darkened room during this period and should be encouraged to expose their skin to ambient indoor light.

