#### NO REASONABLE POSSIBILITY

- The AE is definitely not associated with PDT-Photofrin®;
- The AE does not follow a reasonable temporal sequence from PDT-Photofrin® administration;
- The AE does not disappear or decrease on discontinuation of PDT-Photofrin® (dechallenge) and/or does not reappear or increase on repeated exposure (rechallenge);
- The AE is reasonably explained by known characteristics of the subject's clinical state, history, environment, other therapy administered to the subject (drug or non-drug); and/or
- The AE may be caused by reasons other than administration of PDT-Photofrin®.

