##### 10.5.3. Safety Analysis

Safety analysis will be performed on the Safety Population.

The number and percentage of subjects with normal and abnormal findings will be provided for each physical examination in a shift table comparing screening and the end of study evaluation.

Vital signs will be summarized descriptively (mean, standard deviation, median, minimum and maximum). Change from baseline will also be summarized.

Skin photosensitivity is an adverse event of special interest and will be summarized separately from other adverse events at each safety assessment. Changes in skin will be assessed by grade of erythema, edema and blistering. The data will be tabulated by CTCAE grade in the Dermatology/Skin category.

Descriptive statistics for each clinical laboratory test will be presented for the baseline and the end of study assessment. Change from baseline will also be summarized. According to the laboratory normal ranges, laboratory test results will be categorized as low (< lower limit of normal, LLN), normal (within normal range), and high (> ULN). Shift tables, comparing the distributions of these three categories at baseline versus the end of study assessment, will be presented.

---

Concomitant medications will be coded using the WHO Drug dictionary. Medications initiated prior to start of treatment and maintained during the study, or taken during the course of the study will be considered as concomitant medications. Concomitant medications will be summarized according to the preferred terms only.

Adverse events will be coded using the Medical Dictionary for Regulatory Activities (MedDRA). The number and percentage of subjects who experienced any AEs as well as serious AEs will be presented by system organ class (SOC) and by preferred term (PT) within SOC. All AEs will be similarly presented by intensity (mild, moderate, severe or using the CTCAE grading system) and by relationship to treatment (reasonable possibility/no reasonable possibility). One-sided 95% confidence limit will be computed for each AE percentage via exact binomial method (Clopper-Pearson, 1934).

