5.4.11.1 Adverse Events

Adverse Events will be coded using the Medical Dictionary of Regulatory Activities (MedDRA version 20.0) AE coding system for purpose of summarization.

Events collected at the "NCS Events" CRF page will be summarized together with Adverse Events, but excluded from analyses by CTCAE grade and relationship to study drug, since these data points are not captured for NCS events.

An AE will be defined as treatment-emergent (TEAE) if its date of onset is on or after the date of the study drug (PHO) administration.

An AE will be defined as treatment-related if its relationship to the study drug is recorded as "Reasonable Possibility" on the CRF.

An overall summary of number and percentage of subjects with at least one AE, TEAE, serious TEAE, treatment-related TEAE, serious treatment-related TEAE, TEAE leading to discontinuation and fatal TEAE will be presented.

A summary of the frequency (number and percentage of subjects) of TEAEs will be presented by system organ class and preferred term. One-sided 95% upper confidence limit will be computed for each AE percentage via exact (Clopper-Pearson) method for binomial proportion. Adverse events will also be analyzed by their CTCAE grade (1 to 5) and relationship to study drug (related or not related).

A subject experiencing the same AE multiple times will be counted only once for that preferred term. Similarly, if a subject experiences multiple AEs (preferred terms) within the same system organ class, then that subject will be counted only once for that system organ class. When summarizing by CTCAE grade and relationship, only event with highest grade or relationship will be counted. All AEs will be presented in alphabetical order of SOC and preferred terms.

Skin photosensitivity is an adverse event of special interest (AESI). Skin photosensitivity will be summarized separately by SOC and preferred term as well as by SOC, preferred term and CTCAE grade.

All information pertaining to adverse events noted during the study will be listed by subject, detailing verbatim term given by the investigator, preferred term, system organ class, start date, stop date, CTCAE grade, outcome, action taken and drug relatedness. Separate listings will be created for Serious TEAEs, TEAEs leading to study drug discontinuation and skin photosensitivity events.

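### Exclusion 8 screens out recent PDT to the target tumor only, so a subject with residual photosensitizer from treatment of another lesion is eligible, and that subject's photosensitivity result is confounded

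*Protocol*

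**What the plan says.** Protocol 4.3.2, criterion 8, excludes a candidate if: "Subject has received prior PDT on the tumor scheduled for resection during 3 months prior to the date of the ICF signature". The synopsis has the same wording, so the limit to the target tumor is not a slip in one place.

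Section 7.1 describes photosensitivity as a whole-body effect: "The photosensitivity is due to residual drug, which will be present in all parts of the skin". On duration it says: "Some subjects may remain photosensitive for up to 90 days or more".

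Section 10.5.3 gives the reaction special status: "Skin photosensitivity is an adverse event of special interest and will be summarized separately from other adverse events at each safety assessment". SAP 5.4.11.1 repeats this, and calls any adverse event treatment-emergent "if its date of onset is on or after the date of the study drug (PHO) administration". SAP 5.4.13 lists the Light Challenge result for each subject.

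On earlier treatment, Protocol 4.4 and 4.5 and item 12 of 5.1.2 collect medications and adjunctive procedures from 30 days before consent. Item 3 of 5.1.2 collects medical and oncological history with no look-back limit, without naming PDT or photosensitizers.

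**The concern.** The criterion is tied to where the light was delivered. For the tissue-response endpoint that is the right key, since earlier PDT to the resected tumor could leave necrosis that the pathologist would read as a study effect. For skin photosensitivity, what matters is the injected drug, and by Section 7.1 its distribution in the skin does not depend on which lesion was illuminated.

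A subject who had routine-care Photofrin for another lesion some weeks before consent could therefore enter and receive the study injection while still carrying residual drug. Safety is the primary objective. In that subject a photosensitivity reaction, or a failed Light Challenge, would reflect two exposures but be tabulated as following one study injection.

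**Working it through.** **1. Does any other criterion catch this subject?** Going through Protocol 4.3.2:

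- Criterion 6 covers earlier radiation and is also tied to the tumor to be resected.
- Criterion 7 covers chemotherapy in the last four weeks. The protocol does not describe photosensitizer treatment as chemotherapy.
- Criterion 10 covers porphyria and hypersensitivity.
- Criterion 14 is the nearest: "Subject who participated within the last 30 days, participates or intends to participate in another investigational study (other than observational studies) during the study". It reaches PDT given inside another investigational study, not PDT given as routine care. The synopsis version of criterion 14 lacks the 30-day look-back.

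No criterion excludes routine-care photosensitizer for another lesion, however recent.

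**2. Would the records show the earlier dose?** The medication and procedure look-back is 30 days before consent. Consent and screening fall on Day -30 to Day -1, and the injection is on Day 1. Consent therefore precedes the injection by 2 days (from Day -1) to 31 days (from Day -30). A dose given 31 days before consent is just outside both records and lies 31 + 2 = 33 to 31 + 31 = 62 days before the study injection. Both are inside the 90 days that Section 7.1 mentions. The oncological history may reveal the dose, but no field asks for it. The Light Challenge is first done the day before the Day 43-48 visit, so there is no photosensitivity test before the injection.

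**3. Can the analysis separate the two sources?** The treatment-emergent rule uses onset date alone. Relatedness is the investigator's recorded judgment under Protocol 8.4.2. In the affected subject a reaction could meet an item on the unrelated list, "The AE may be caused by reasons other than administration of PDT-Photofrin", and also an item on the related list, since it is a known effect of the treatment. The SAP has no rule that identifies such a subject.

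**4. Size.** The plan's measure is the one-sided 95% exact upper limit with n = 10, the p that solves P(X ≤ x | n = 10, p) = 0.05. For x = 0 this is 1 − 0.05^(1/10) = 0.2589. For x = 1 to 5, solving numerically gives 0.3942, 0.5069, 0.6066, 0.6965 and 0.7776. All six agree with the table in Protocol 10.1 (0.26, 0.39, 0.51, 0.61, 0.70, 0.78). SAP 5.4.11.1 applies this limit to every adverse event percentage, so it applies to photosensitivity too.

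Effect of one subject's event:

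- 0/10 to 1/10: rate +10 points, limit 0.259 to 0.394 (+0.135).
- 1/10 to 2/10: rate +10 points, limit 0.394 to 0.507 (+0.113).
- Leaving the subject out: 0/9 gives 1 − 0.05^(1/9) = 0.283, and 1/9 gives 0.429.

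**5. How likely is such a subject?** The documents give no figure. If a share q of enrolled subjects had recent photosensitizer for another lesion, the chance of at least one among 10 is 1 − (1 − q)^10. Assumed values of q = 1%, 2%, 5% and 10% give 9.6%, 18.3%, 40.1% and 65.1%. These are assumptions, not estimates.

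**The case against.** A reader might infer that photosensitivity can no longer be attributed to the study injection in this trial. The documents do not support that. Subjects without earlier photosensitizer are unaffected. In the affected subject attribution is confounded, not impossible: Section 7.1 says every Photofrin recipient will be photosensitive, so a reaction soon after a fresh injection remains reasonably attributable to it.

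Nor is the move from 0.26 to 0.39 an expected bias. It needs a reaction that residual drug caused and the fresh dose would not have caused, which is hard to argue when the fresh dose alone makes the subject photosensitive. The complications tabulated in Protocol 10.1 are also those of radiofrequency ablation. Photosensitivity is not among them.

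The case is probably rare. Section 1.3 gives the approved lung indications as microinvasive endobronchial disease in patients for whom surgery and radiotherapy are not indicated, and palliation of obstructing endobronchial disease. This trial enrolls candidates for complete resection of a peripheral tumor, so overlap looks small. Section 5.2.1.2 says "Subjects presenting multiple metastases, only one lesion would be treated", which shows that subjects with several lesions can enter. It does not show that any of those lesions had recent PDT.

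There are safeguards. Oncological history is collected without a time limit, and SAP 5.4.4 summarizes and lists it. The sponsor's medical monitor approves each enrollment, and eligibility is checked again before injection. Adverse events are recorded from consent, so a reaction that starts before the injection is not treatment-emergent. Photosensitivity events and Light Challenge results are listed by subject, and with 10 subjects an unusual one can be seen.

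All of this stands and limits the size of the point. It does not close the gap: the safeguards may reveal such a subject but give no criterion for exclusion, and no field marks the earlier dose in the listings.

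**Conclusion.** The point holds as a gap in eligibility and recording, at modest priority. Exclusion 8 protects the secondary tissue-response endpoint from earlier PDT but leaves the primary safety endpoint open to carry-over from photosensitizer given for another lesion, and it does not fit with Section 7.1. The consequence is confined to an affected subject, whose photosensitivity events and Light Challenge result would reflect two exposures. One such event is worth 10 percentage points of a rate based on 10 subjects, and 0.11 to 0.14 on the upper limit at the low counts shown, if it would not have occurred from the study injection alone.

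This rests on two assumptions: that a candidate could have had routine-care systemic photosensitizer within the period Section 7.1 describes, and that neither the history nor the medical monitor's review would keep that candidate out. The documents neither rule this out nor say how often it would happen.

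**What to change.** Reconcile exclusion 8, in 4.3.2 and in the synopsis, with Section 7.1 by extending it to prior systemic photosensitizer given for any lesion. The sponsor should set the interval and the date from which it is counted; none is proposed here. Keep prior PDT to the target tumor as a separate clause, since it serves the tissue-response endpoint.

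Add a line to the Eligibility Verification Form and CRF for any earlier photosensitizer exposure and its date, not limited to the 30-day look-back. Show that entry beside the skin photosensitivity events and Light Challenge results in the SAP listings. A subject whose earlier exposure falls outside the chosen interval, or who enters by deviation, can then be identified.

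The cost is one amended sentence, one form line and the occasional loss of a candidate recently treated elsewhere.
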